8.4 Replacement of Patients

Patients who withdraw their consent or are screen-failed prior to randomization, will be replaced to ensure that at least 264 patients with a Health Status of 3 or 4 enroll in the Phase 3 confirmatory portion of the study. Patients who withdraw (study or further treatment) after randomization will not be replaced.

9 STUDY CONDUCT

9.1 Timing of Assessments

For the sake of simplicity, the timing of assessments is not specified. Investigator and their staff should however use their judgment to avoid the interference of more invasive procedures on sensitive procedures.

9.2 Study Visits and Procedures

9.2.1 Screening and Eligibility Assessments (Visit 0, pre-randomization on Day -1 or (no Day 0 in this study)):

Prior to randomization, potentially eligible and interested patients will undergo the following:

- 1. Verification of identity and age;
- 2. Prior to any study specific screening activities, all potential patients will sign the Study Informed Consent Form (ICF), since paper copies are deemed contaminated, it is possible to take a picture of the signed page when possible. The consent can also be obtained verbally per COVID-19 regulatory requirements or local recommendations and use a witness to attest of the verbal consent. The consent forms will comply with all applicable regulations governing the protection of human subjects. An ICF Form, approved by Laurent Pharmaceuticals and the site's institutional review board (IRB or REB, as applicable), must be used. At this point, the patient's initials are used for identification purposes and to identify the patient at the time of randomization in the IWRS. The IWRS will issue the Subject Number (Randomization Number); it will be used from that point forward for the entire study participation, to identify the patient.
- 3. Verification of all inclusion and exclusion criteria:
- 4. Obtain demographic information and recent & relevant medical history (typically the previous 6 months). Particular attention will be put on confirming the underlying disease or factors (including COVID vaccination) susceptible to affect the prognosis of COVID-19 disease progression and used to determine eligibility;
- 5. Verification of the concomitant medications, including any supplemental oxygen currently in use, along with recording the oxygen flow in use;
- 6. Body weight, height, with BMI calculated (measured if possible but self-reporting is accepted);
- 7. Directed physical examination (symptom- and disease-driven);
- 8. From SOC, collect the vital signs including heart rate, respiratory rate, oxygen saturation (under room air if possible, or value obtained prior to administering supplemental oxygen, from patient chart) and body temperature;
- 9. COVID-19 symptom check (including but not limited to, fever, myalgia, coughing, dyspnea, smell and taste alteration, headache, gastrointestinal disorders...etc.) as per SOC;
- 10. SOC laboratory tests including at a minimum, urinalysis (dipstick), hematology, serum chemistry (while they should be preferably done during the screening, it is acceptable that they be obtained from the Standard-of-Care performed between the start of hospitalization and screening but in no case more than 48 hours prior to screening; with the exception that when a patient is only eligible based on an abnormal biomarker (troponin, D-dimer or CRP, for example), such a value should have been obtained no more than 24 hours prior to screening) and urine (or serum) pregnancy test if applicable (details on the

minimum laboratory testing can be found in Section 11.2). The pregnancy test result must be available before randomization and it must be negative;

- 11. Health status determination using the 7-point ordinal scale;
- 12. Quality-of-Life questionnaire: EQ-5D-5L questionnaire.

The clinical site or Investigator may request additional procedures/tests that are part of the COVID-19 disease SOC at the institution or are required based on the patient's condition; these will not be captured in the CRF but should be recorded in the patient's source documentation.

9.2.1.1 Repeat performance of screening assessment(s)

Repeat of individual screening assessment(s) that did not meet eligibility criteria is not permitted unless there is clear and documented evidence of a laboratory error (e.g., hemolyzed sample) or equipment malfunction. If the repeat values of the individual assessment(s) are within the eligibility criteria and completed before randomization, then the patient is eligible for the study.

9.2.1.2 Rescreening

Not applicable.

9.2.2 Randomization and First Dosing (Visit 1, Day 1)

It is expected and desirable that once all screening procedures are complete and eligibility is confirmed, that the patient transitions directly to randomization, without delay. Randomization will be performed on the IWRS platform and the assigned Initial treatment container (9 capsules) will be retrieved from the pharmacy (where applicable) and stored in the ward's refrigerator, as per site procedures.

Randomized patients will receive their first dose of 3 capsules of study treatment, under fed condition. As patient is hospitalized, there is no mandatory supervision period.

9.2.3 In-Hospital Days

For this study in hospitalized patients with confirmed COVID-19 disease, the hospital stay duration will vary as a function of complications/improvement observed with each given patient, the bed and resources availability, rules and restrictions imposed by Health Authorities (Institution, Governmental...etc.). In order to minimize the burden of this study on the hospital resources, the in-hospital study requirements will piggyback on the SOC, with some exceptions. The overall scheme can be found in the Schedule of Event on page 11. Details are presented below.

1. Pre-Dose on Day 4 only:

If the patient has tolerated the Initial treatment of 3 days, if not done previously, a replenishment will be requested in the IWRS and the Follow-up treatment container (22 capsules) will be retrieved from the pharmacy (where applicable) and stored in the ward's refrigerator.

- 2. On Days 5, 8 and 12 (visits 5, 8 and 12, with a window of +/- 1 day while in hospital), the following assessments will be done:
 - a. Concomitant medication verification, including any supplemental oxygen currently in use;
 - b. Directed physical examination (symptom- and disease-driven);
 - c. From SOC, collect the vital signs including heart rate, respiratory rate, oxygen saturation and body temperature (can be done multiple times during each day as part of SOC, but at a minimum twice);

- d. COVID-19 symptom check (including but not limited to, fever, myalgia, coughing, dyspnea, smell and taste alteration, headache, gastrointestinal disorders...etc.) as per SOC;
- e. SOC laboratory tests including at a minimum, urinalysis (dipstick), hematology and serum chemistry, as per Section 11.2 (the laboratory test can be performed within +/- 1 day from the target visit day);
- f. Health status determination using the 7-point ordinal scale;
- g. Handing study medication for intake during the main meal of the day;
- h. Asking safety-focused open-ended questions:
 - i. How is your health today?
 - ii. How is your vision today?
 - iii. How is your skin today?
- i. Adverse event verification and follow-up on ongoing adverse events.

3. On Day 14 or on the Day of hospital discharge (not a preset visit number), the following assessments will be done:

- a. Concomitant medication verification, including any supplemental oxygen currently in use;
- b. Directed physical examination (symptom- and disease-driven, will not be repeated if assessment done within 2 days from the discharge day);
- c. Body weight with BMI calculated (measured if possible);
- d. From SOC, collect the vital signs including heart rate, respiratory rate, oxygen saturation and body temperature;
- e. COVID-19 symptom check (including but not limited to, fever, myalgia, coughing, smell and taste alteration, headache, gastrointestinal disorders...etc.) as per SOC;
- f. SOC laboratory tests including at a minimum, urinalysis (dipstick), hematology and serum chemistry (will not be repeated if assessment done within 2 days from the discharge day), as per Section 11.2;
- g. Urine (or serum) pregnancy test if applicable;
- h. Health status determination using the 7-point ordinal scale;
- i. Quality-of-Life questionnaire: EQ-5D-5L questionnaire;
- j. If applicable, dispensing to the patient the remaining study drug treatment with instructions for storage in the home refrigerator, self-administration, and return of unused study drug in a prelabeled envelope;
- k. Asking safety-focused open-ended questions:
 - i. How is your health today?
 - ii. How is your vision today?
 - iii. How is your skin today?
- 1. Adverse event verification and follow-up on ongoing adverse events.

4. On all other Days in Hospital until the day before discharge or before Day 14 (Visit numbers = Day of the study): The following assessments will be done:

- a. From SOC, collect the vital signs including heart rate, respiratory rate, oxygen saturation and body temperature (can be done multiple times during each day as part of SOC, but at a minimum twice);
- b. COVID-19 symptom check (including but not limited to, fever, myalgia, coughing, smell and taste alteration, headache, gastrointestinal disorders...etc.) as per SOC;
- c. Health status determination using the 7-point ordinal scale;
- d. Handing study medication for intake during the main meal of the day;
- e. Adverse event verification and follow-up on ongoing adverse events.

5. Early-Termination Visit

This visit may happen anytime a patient elects to withdraw consent or becomes unable to be followed-up, as detailed in Section 8.3. The following assessments can be performed, sometimes indirectly since the patient may not be able to contribute.

- a. Concomitant medication verification, including any supplemental oxygen currently in use, including the oxygen flow;
- b. If possible, collect the vital signs including heart rate, respiratory rate, oxygen saturation and body temperature;
- c. Urine (or serum) pregnancy test if applicable;
- d. Adverse event verification and follow-up on ongoing adverse events.

9.2.4 Contacts in hospital after Day 14 or after discharge once every 3 days (±2 days from target) and up to Day 29

(not a preset visit number)

The following assessments will be done, either at the hospital, or by phone or using an electronic platform compatible with mobile phones or tablets.

- e. Concomitant medication verification, including any supplemental oxygen currently in use including the oxygen flow;
- f. COVID-19 symptom check (including but not limited to, fever, myalgia, coughing, smell and taste alteration, headache, gastrointestinal disorders...etc.) as per SOC;
- g. Health status determination using the 7-point ordinal scale;
- h. Verification of the study drug intake and accountability, where applicable;
- i. Asking safety-focused open-ended questions:
 - i. How is your health today?
 - ii. How is your vision today?
 - iii. How is your skin today?
- i. Adverse event verification and follow-up on ongoing adverse events.

9.2.5 Contacts on Days 29 and 45 (window of +/- 3 days)

(not a preset visit number)

The following assessments will be done, either by phone or using an electronic platform compatible with mobile phones or tablets. Based on the patient responses, actions may be taken including inviting the patient to visit the hospital or meet a health professional.

- a. Concomitant medication verification, including any supplemental oxygen currently in use including the oxygen flow;
- b. COVID-19 symptom check (including but not limited to, myalgia, coughing, smell and taste alteration, headache, gastrointestinal disorders...etc.) as per SOC;
- c. Health status determination using the 7-point ordinal scale;
- d. Quality-of-Life questionnaire: EQ-5D-5L questionnaire;
- e. Asking safety-focused open-ended questions:
 - i. How is your health today?
 - ii. How is your vision today?
 - iii. How is your skin today?
- f. Adverse event verification and follow-up on ongoing adverse events.

9.2.6 End-of-Study / Long-term Follow-up

(Day 60 (window of +/- 3 days) after randomization, not a preset visit number)

The following assessments will be done, either by phone or using an electronic platform compatible with mobile phones or tablets.

- a. COVID-19 symptom check (including but not limited to, myalgia, coughing, smell and taste alteration, headache, gastrointestinal disorders...etc.) as per SOC;
- b. Health status determination using the 7-point ordinal scale;
- c. Quality-of-Life questionnaire: EQ-5D-5L questionnaire;
- d. Adverse event verification and follow-up on ongoing adverse events.

9.3 Study Drug Treatment

The total duration of study treatment is up to 14 consecutive days of either LAU-7b or placebo, as follows:

Eligible patients will be randomized (1:1) to receive in a blinded fashion, either LAU-7b 300 mg per day (3 capsules of 100 mg each), once a day for 3 days, or a matching placebo administered in the same fashion (the "Initial Treatment").

From Day 4, patients will continue the treatment with LAU-7b 200 mg per day (2 capsules of 100 mg each), once a day for the remaining 11 days, or a matching placebo administered in the same fashion (the "Follow-up Treatment").

All eligible and confirmed patients will be treated and closely monitored for a period of up to 2 weeks or until early termination. The last day of study drug treatment will be on Day 14 or earlier due to aggravation preventing oral intake of study medication or death, whichever comes first. Specifically, patients undergoing intubation preventing oral intake of study medication will not receive the drug by other means such as through a feeding tube. Patients will continue their study participation as planned except for procedures that cannot be performed due to disease aggravation.

In all cases, the study treatment will be administered on top of current SOC therapies for COVID-19 disease.

9.3.1 LAU-7b (fenretinide)

It consists of an orange opaque, size 00, hard gelatin capsule containing 100 mg of fenretinide. The formulation contains the following non-medicinal ingredients

The capsules are dispensed in HDPE bottles containing either 9 capsules (Initial Treatment) or 22 capsules (Follow-up Treatment). Study medication will be handled as follows:

- Shipped refrigerated (2 to 8°C, 36-46°F) to the Hospital pharmacy;
- Stored refrigerated (2 to 8°C, 36-46°F) in the Hospital pharmacy and wards, and where applicable,
- Stored refrigerated (2 to 8°C, 36-46°F) at the patient's home.

9.3.2 Placebo

A matching orange opaque, size 00 hard gelatin capsule without fenretinide will be used as a placebo for blinding purposes and will contain the same non-medicinal ingredients.

The capsules are dispensed in HDPE bottles containing either 9 capsules (Initial Treatment) or 22 capsules (Follow-up Treatment). Study medication will be handled as follows:

• Shipped refrigerated (2 to 8°C, 36-46°F) to the Hospital pharmacy;

- Stored refrigerated (2 to 8°C, 36-46°F) in the Hospital pharmacy and wards, and where applicable,
- Stored refrigerated (2 to 8°C, 36-46°F) at the patient's home.

9.3.3 Packaging, Labeling, and Shipping

Study medication will be provided in appropriately-sized HDPE bottles containing enough medication for either the Initial Treatment phase (9 capsules) or the Follow-up Treatment phase (22 capsules). Study drug will be specifically identified and bear instructions to ensure proper intake. The details will be described in the Pharmacy Manual.

Shipments will be done using a Sponsor-defined courier, under refrigerated temperature (target 2 to 8°C, 36-46°F), a temperature data logger may accompany the shipment to ensure an adequate chain of custody.

9.3.4 Storage, Dispensing and Compliance Verification of Study Drug

Upon receipt of the study drug shipper container, the investigator should record the receipt, date, time, and temperature of the product based on inspection or on the temperature logger reading, where applicable. Any study drug that arrives in improper storage conditions or is damaged in any way must be reported to the Laurent designee, as instructed in the Pharmacy Manual, as soon as possible and shall not be administered until instructed otherwise.

At the clinical sites, the study drug bottles will initially be stored in a suitable refrigerator (2 to 8°C, 36-46°F) in a secure location with limited access. Most preferably, the storage refrigerator will be continually monitored and alarmed in order to document any excursion outside the desired temperature range. Alternatively, the use of a calibrated min-max thermometer in the storage refrigerator is acceptable as long as the thermometer readings are taken daily during weekdays, at a minimum. On the hospital ward, the drug should also be stored in the refrigerator, and most preferably, also monitored similarly.

Upon instructions from the IWRS, the pharmacy/site staff will, at the time of dispensing, formally identify and remove the assigned treatment bottle from the secure refrigerator and will check the expiry date on the labels, at a minimum. Where applicable, the necessary treatment bottle will be sent to the site staff on the ward actually dispensing the study drug to the patients.

To avoid incorrect patient dosing, the instructions/paperwork/bottles must bear clearly the "subject number" and site staff **must be trained** to **correlate the treatment bottle with the target patient**, since there will be multiple patients active on the study medication at any point in time.

The study drug may only be used as directed in this RESOLUTION protocol. It is against regulations to use investigational products for other purposes.

9.3.5 Administration of Study Drug Treatment

On each inpatient Day at the Hospital, the patient will be handed the required quantity of capsules to ingest with the main meal of the day (if possible). The capsules should not be broken down to administer their content through a feeding tube if the patient is intubated and cannot ingest anymore the capsules intact. If the patient is discharged from the clinical site before Day 14 (the last day of study drug intake), the patient will be dispensed the remaining capsules of study drug and will receive instructions to continue the intake until Day 14.

9.3.6 Study Drug Reconciliation and Destruction

Investigators must maintain accurate records regarding the receipt, dispensing, and where applicable, return or destruction of study drug for each patient in the study. Patients discharged from hospital prior to the end of study drug treatment will be given a pre-labeled+paid return envelope and will be instructed to keep the

bottle and any content remaining after completing the study drug intake until the next phone contact, which will enable a verbal reconciliation. Patients will then be instructed to return the study medication in the provided envelope. At the site, any used study drug containers, as well as any unused containers or unused portions of containers, must be maintained until accounted for by the monitor. After accountability by the monitor and approval from the sponsor, the study drug and containers should be destroyed per the site's SOP for destruction of biological waste or returned to the Sponsor or Sponsor designee for disposition.

9.4 Treatment and Protocol Compliance

Patients are expected to receive oral daily doses based on the protocol schedule and have all procedures done within the allowable time windows (outlined in the Schedule of Events, page 11 and further detailed in Study Visits and Procedures).

Regardless of allowable visit windows, study drug treatment should target a total of 14 days. In the event a patient misses an outpatient dose, he/she should not double-dose on the next dosing day; instead, he/she should continue as planned and take a note of this omission for disclosure at the next outpatient contact.

In the event a patient misses a scheduled in-hospital/outpatient contact, this should be rescheduled for the earliest possible date. Patients who are persistently noncompliant may be withdrawn from the study at the investigator's or the sponsor's discretion.

9.5 Allowed and Disallowed Concomitant Medications

The standard of care for patients with COVID-19 disease is continually evolving and may include several medications and procedures destined to improve their outcome, treat symptoms and prevent aggravation. Considering the very short study treatment duration and the lack of clinically proven drug interactions for fenretinide, there is only a limited number of disallowed medications for this study. The COVID-19 SOC should be used, with the following restrictions, always weighing the risk versus benefit of co-administration. Co-enrolment in other interventional studies of unproven COVID-19 treatments is not permitted.

Based on the available *in-vitro* and *in-vivo* data from animal studies and human clinical trials, the short term fenretinide treatment in the RESOLUTION study (only 14 days) is not expected to cause any clinically significant Drug-Drug Interactions in COVID-19 patients with concomitant administration of most commonly used drugs for diseases such as Type-2 diabetes, hypertension or asthma, some being metabolized by CYP enzymes. There is no real risk either for clinically significant interactions with drugs potentially added to SOC, such as remdesivir and dexamethasone, for the same reasons. Furthermore, since fenretinide is marginally eliminated in urine and eventually co-administered antibiotics are mostly eliminated by the kidneys, the risk of interactions with these drugs is improbable.

9.5.1 Disallowed medications:

After consulting the Study Reference Manual, in case of doubt about a patient's concomitant medication, study personnel should consult with the Sponsor's representative before enrolling/pursue participation of a patient on study.

- 1. Concomitant use of Narrow Therapeutic Index drugs that are sensitive CYP substrates (e.g.: amiodarone, carbamazepine, cyclosporine, digitoxin, theophylline, phenytoin, warfarin, etc. See list in study reference manual) is authorized but the adverse events of these drugs should be monitored as per standard of care. In the study so far, the following drugs were co-administered with LAU-7b with no relevant adverse events: amiodarone (3 patients), carbamazepine (1 patient) and warfarin (1 patient);
- 2. Concomitant use of known strong inducers or inhibitors of hepatic CYP450 isoenzyme (e.g.: ketoconazole, fluoxetine, clopidogrel, rifampin, etc. See list in study reference manual) is authorized but the known adverse events of fenretinide should be monitored. In the study so far, the following drugs

- were co-administered with LAU-7b with no adverse events: fluconazole (2 patients), fluoxetine (1 patient) and clopidogrel (4 patients);
- 3. Concomitant use of medications that may potentially act as modulators of intracellular ceramide levels or ceramide cytotoxicity, sphingolipids transport, or p-glycoprotein "MDR1" or "MRP1" drug/lipid transporters, such as: cyclosporine A or analogue; verapamil; tamoxifen or analogue; ketoconazole, chlorpromazine and thioridazine; RU486 (mifepristone); indomethacin; or sulfinpyrazone continue to be prohibited. In the study so far, the prohibition was respected.

While the concomitant use of drugs known to prolong QT significantly is permissible in this study, only in the event that such a drug is already used or planned to be added, the cardiac safety of the combination should be monitored by performing 12-lead ECG during the stay in the hospital; specifically, either before starting the study medication (can be obtained from SOC within 48 hours prior to screening) or before adding the QT-prolonging drug to the study medication, and approximately once every 2-3 days thereafter during the hospital stay. Appropriate actions may be taken subsequent to QT prolongation from baseline exceeding 50 msec or a treatment-emergent QT segment exceeding 500 msec. In the study so far, the following drugs were co-administered with LAU-7b with no relevant adverse events or ECG abnormalities including QT prolongations reported as adverse events: azithromycin (23 patients including 6 who also took another drug prolonging the QT segment), ciprofloxacin (2 patients including one who also took citalopram), citalopram ((2 patients including one who also took citalopram), citalopram (18 patients including 4 who also took another drug prolonging the QT segment). ECG monitoring will continue to be recommended in the study expansion when a known QT prolonging drug is started on-study or is part of a patient's regimen at baseline.

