12.4 Estimand Strategy

Some types of intercurrent events are expected to possibly occur during the course of the study: treatment interruption; treatment discontinuation; and use of disallowed medication (see Section 9.5.1). The project estimands strategies, including those for handling each of these types of intercurrent events are summarized in Table 3 below.

Table 3: Primary Objective and Estimands with Rationale for Strategies to Address Intercurrent Events in Phase III

Objective: To evaluate the efficacy of LAU-7b therapy + Standard-of-Care (SOC) relative to placebo + SOC in patients with COVID-19 disease with confirmed SARS-CoV-2 infection.			
Target Population	Adult subjects with COVID-19 disease with confirmed SARS-CoV-2 infection and a Health Status score 3 or 4 at baseline.		
Variable/Endpoint	The 7-point ordinal scale of the patient status / The proportion of patients requiring mechanical ventilation AND/OR deceased (all causes) by Day 60		
Primary Estimand			
Intercurrent events 1.Treatment Interruption 2.Treatment Discontinuation for Other Reasons than death 3.Use of Disallowed Medication	Treatment Policy strategy	1. For temporary interruptions of study treatment (e.g. due to an adverse event), data collected will be analyzed as if treatment had continued normally throughout the study. If the treatment is interrupted and then never restarted (e.g. due to subject death, withdrawal) then it will be treated as per treatment discontinuation strategies below. 2. For endpoints where the subject has data available, the subject will continue to be analyzed as part of their treatment group even if they have discontinued treatment. Missing data are not considered part of this intercurrent event and are handled separately (see the appropriate Section 12.7 or 12.8 for handling depending upon endpoint). 3. If a subject is given disallowed medication (see Section 9.5.1) after enrollment, their safety and efficacy data will be analyzed as normal.	
Intercurrent events 4. Treatment Discontinuation due to Lack of Efficacy (mechanical ventilation) or Safety Event (death)	Composite event strategy	4. Serious safety events and/or indications of lack of efficacy (e.g. death, mechanical ventilation) are included in study endpoints as part of analyses. Therefore, treatment discontinuation due to most anticipated types of safety/lack of efficacy events are accounted for in the endpoints and analyses	

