16.2 Protocol Amendment

Administrative amendments to the protocol will be classified as amendments of typographical errors, clarifications of confusing wording, name changes, and minor modifications that have no impact on the safety LAU-7b for the treatment of COVID-19 disease in Adults

Amendment 5, V2.4, Aug 4th, 2023

71 of 79

of the patients or the science of the study. Administrative amendments will be submitted to the IRB/IEC for information only. Laurent Pharmaceuticals will ensure that acknowledgement is received and filed. Any other amendment will be classified as a substantial amendment and will be submitted to the appropriate regulatory authorities and the IRBs/IECs for approval.

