16.3 Protocol Deviation

Should a protocol deviation occur, Laurent Pharmaceuticals must be informed as soon as possible. Important protocol deviations and their reasons will be summarized in the clinical study report. In accordance with applicable regulatory authority mandates, the investigator is responsible for reporting protocol deviations to the IRB/IEC.

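### Section 9.5.1 authorizes cyclosporine in item 1 and ketoconazole in item 2, prohibits both in item 3, and does not say which item prevails

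*Protocol*

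**What the plan says.** Section 9.5.1 of the protocol is headed as a list of disallowed medications and has three numbered items.

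- **Item 1** covers narrow-therapeutic-index drugs that are sensitive CYP substrates. Its examples and status read: "amiodarone, carbamazepine, cyclosporine, digitoxin, theophylline, phenytoin, warfarin, etc. See list in study reference manual) is authorized". The condition is that the adverse events of those drugs are monitored under standard of care.
- **Item 2** covers strong inducers or inhibitors of hepatic CYP450 enzymes. Its examples and status read: "ketoconazole, fluoxetine, clopidogrel, rifampin, etc. See list in study reference manual) is authorized". The condition is monitoring for the known adverse events of fenretinide.
- **Item 3** covers drugs that may modulate ceramide levels or toxicity, sphingolipid transport, or certain drug and lipid transporters. Its examples include "cyclosporine A or analogue; verapamil; tamoxifen or analogue; ketoconazole, chlorpromazine and thioridazine", followed by mifepristone, indomethacin and sulfinpyrazone. Their status is that they "continue to be prohibited. In the study so far, the prohibition was respected".

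The lead-in to the list begins "After consulting the Study Reference Manual, in case of doubt about a" patient's medication. It then tells staff to ask the sponsor's representative before enrolling the patient or continuing participation.

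Section 12.4 (Table 3) treats use of disallowed medication as an intercurrent event and points to Section 9.5.1 for its definition: "If a subject is given disallowed medication (see Section 9.5.1) after enrollment, their safety and efficacy data will be analyzed as normal".

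**The concern.** The same list tells a site that it may give cyclosporine or ketoconazole with monitoring, and that it may not give them at all. A reader looking up ketoconazole finds it first in item 2, with a complete instruction and no prompt to read on to item 3. Following item 2 exactly would mean giving a drug that item 3 bars.

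Four things depend on the answer:

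- **Site conduct.** Whether either drug may be given alongside the study drug.
- **The intercurrent-event flag.** Section 12.4 has no definition of disallowed medication other than Section 9.5.1, which gives both answers for these two drugs.
- **Deviation coding.** One site's use could be recorded as permitted and another's as a deviation.
- **Per-protocol membership.** Section 12.3 requires freedom from major protocol deviations identified before database lock. Membership could therefore turn on the coding, but only if such a use were rated major.

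**Working it through.** The plan states no figure on this point, so the check is a comparison of text plus a simple count.

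**Step 1. Set the items side by side.**

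| Drug | Item 1 | Item 2 | Item 3 |
|---|---|---|---|
| Cyclosporine | authorized, with monitoring | not named | prohibited (as cyclosporine A or an analogue) |
| Ketoconazole | not named | authorized, with monitoring | prohibited |

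Ketoconazole is named identically in items 2 and 3. Item 1 says cyclosporine where item 3 says cyclosporine A. Item 3 also extends to analogues, so its wording covers the item 1 drug.

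These are the only two overlaps among the named examples. Items 1 and 2 end their example lists openly and refer to a list in the manual, and item 3 gives its drugs as examples. Two is therefore the overlap visible in the protocol, not necessarily the full overlap, and it carries no information about how often either drug would be used.

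**Step 2. Look for a rule that ranks the items.**

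- Sections 9.5 and 9.5.1: no sentence says which item prevails, and nothing removes the two drugs from items 1 and 2. The nearest provision is the lead-in, which gives a consultation route but no ranking.
- Sections 8.2 (exclusion criteria) and 8.3 (discontinuation and withdrawal): neither settles the status of these drugs.
- Section 12.4: it refers back to 9.5.1 without resolving the overlap.
- SAP Addendum: it does not address the matter.

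**Step 3. Check reported experience.** Items 1 and 2 report drugs co-administered with LAU-7b up to the time of writing:

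- Item 1: amiodarone 3 + carbamazepine 1 + warfarin 1 = 5.
- Item 2: fluconazole 2 + fluoxetine 1 + clopidogrel 4 = 7.
- Total: 5 + 7 = 12, of which cyclosporine or ketoconazole = 0.

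These are drug-by-patient counts, so one patient could appear more than once. Item 3 adds that its prohibition had been respected to date.

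**Step 4. Trace the effect on the primary analysis.** Table 3 assigns disallowed medication to a treatment-policy strategy, so the data of a patient who takes such a drug are analysed in the usual way. Recoding a use from permitted to disallowed, or the reverse, moves no patient into or out of the primary intent-to-treat comparison and changes no outcome. The effect on that result is nil.

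**The case against.** The best defence is that the three items are cumulative. Items 1 and 2 relax a concern about CYP metabolism. Item 3 bars drugs on a separate ground, and its wording marks the ban as one that remains in force. On that reading, being acceptable on CYP grounds does not lift a ban on other grounds, and the two drugs are simply poorly chosen examples. This is probably what was intended. But it is an inference: items 1 and 2 are not silent on these drugs, and each names one and authorizes it.

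A second defence is the consultation route. Staff go first to the manual and, if unsure, to the sponsor's representative. This is a real safeguard. Its limit is that it depends on someone being unsure, and a drug listed by name as authorized may raise no question. The manual may state the status correctly; it is not among the documents, so the actual effect at sites cannot be judged. Even if it does, the protocol text still contradicts itself.

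A third defence is that no harm is visible. That stands for what is reported: no co-administration of either drug, and item 3 respected. It describes experience only up to the date of the protocol version.

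A reader might infer more than this supports. One tempting reading is that prohibited drugs were actually given, or that sites were misled. The documents show no such case and give no basis for projecting a number. Another is that the efficacy conclusion is in question. Table 3 rules that out for the primary intent-to-treat analysis.

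**Conclusion.** The contradiction is in current, intact text, and the point stands as a minor one. Two named drugs are each both authorized and prohibited, and no written rule decides between the two instructions. The consequences are confined to site instructions, the disallowed-medication flag, deviation coding and, if a use were rated a major deviation, per-protocol membership. The effect on the primary intent-to-treat result is nil.

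The conclusion that the text conflicts rests on the protocol alone. Any conclusion about practical impact would depend on the Study Reference Manual, which was not available. That item 3 is the intended rule is an assumption drawn from its wording.

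**What to change.** Delete cyclosporine from the item 1 examples and ketoconazole from the item 2 examples. Alternatively, add one sentence to Section 9.5.1: *A drug covered by item 3 is prohibited even if it also falls under item 1 or 2.* The added sentence has the advantage of also covering overlaps hidden in the open-ended lists. In either case, check that the lists in the Study Reference Manual agree.

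The cost is two deleted words or one sentence, plus the check of the manual. Section 16.2 counts clarification of confusing wording as administrative, and if the change is classed that way, "Administrative amendments will be submitted to the IRB/IEC for information only".

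The SAP Addendum (Section 1) records that the planned analyses were completed after database lock, so an edit to Section 9.5.1 can no longer change conduct in this study. What remains is to apply the item 3 status when classifying any use of either drug as a deviation. Section 16.3 already provides a place for any that are important: "Important protocol deviations and their reasons will be summarized in the clinical study report". Concomitant medications are already collected and coded under Section 12.6.1, so this needs no new data. A separate drug-by-drug statement in the report would be optional.
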